## 5. Description of Protocol Assessments & Procedures

### 5.1. Informed Consent and HIPAA Authorization

Written informed consent will be obtained from each subject before any study-related procedures may commence. Informed consent will be obtained by the investigator or designee at each study site. A notation will be made in the subject's case history/medical chart that he/she is participating in a clinical study and has been provided a signed and dated ICF as well as the required site HIPAA authorization (if separate from the ICF).

### 5.2. Inclusion/Exclusion Criteria

Site staff and the investigator will document the date of ICF signature and review all of the inclusion and exclusion criteria with respect to the potential subject in question. Review of

criteria may require sites to review the potential subject’s medical records or ask questions of the potential subject. All questions relevant to the visit must be answered at that visit for the subject to be able to proceed with that and future visits.

### 5.3. Medical Resource Utilization (MRU)

Standardized assessments to document MRU (e.g., physician services, treatment/procedures, medications, etc.) required to manage the subject’s current DFU will be performed by a review of the subject’s source document/medical record and by the investigator or designee completing an interview with the subject.

The MRU assessment should be performed prior to any other study procedures or assessments in order to minimize bias.

The following information will be collected related to the DFU and its care:

- Physician office visits
- Emergency room visits
- Hospitalizations
- Home health nursing visits
- Skilled nursing facilities
- Procedures
- Diagnostic tests, imaging, etc.
- Treatment of AEs
- Interference with activities of daily living
- Interference with paid work (full-time or part-time)/school
- Use of durable medical equipment (e.g., off-loading/protective device, crutches, wheelchair, etc.)
- Dressing regimen and materials

### 5.4. Baseline Demographics

For the purposes of this study, demographic information will include:

- Date of birth
- Gender
- Race
- Ethnicity
- Use of nicotine products
- Use of alcohol

### 5.5. Medical History

The site will assess and document the DM type (Type 1 or Type 2) and date/year of diagnosis. Subject’s HbA1c level and date of test must be recorded (**Note: The test results must be valid within 3 months of SV1 and must be in existence on SV1**).

In addition to diabetic status, additional medical history that, in the opinion of the investigator, is **relevant to the safety of the subject or that could impact diabetic foot ulcer healing** is to be recorded (i.e., obesity, neuropathy, etc.).

Relevant medical histories will be recorded using the body system categories outlined below:

- Cardiovascular
- Lymphatic
- Respiratory
- Hematologic
- Gastrointestinal
- Immunologic
- Renal
- Dermatologic
- Hepatic
- Psychiatric
- Neurological (Including Neuropathy)
- Genitourinary
- Endocrine
- Other

For each relevant medical history, the following will be documented:

- Condition (i.e., name of disease/disorder)
- Medical History Category (e.g., general medical history, surgical procedure, other)
- Date/ Year of Onset
- Status (i.e., resolved or ongoing)

## 5.6. Physical Examination

The physical examination will include routine examinations for the following:

- Abnormalities of the extremities
- Neurologic abnormalities (Including Neuropathy)
- Heart/cardiovascular abnormalities
- Musculoskeletal abnormalities
- Dermatologic abnormalities
- Other abnormality (i.e., any other body system for which an abnormality is noted and which, in the opinion of the investigator, is relevant to the safety of the subject or could impact ulcer healing should be considered clinically significant.)
- Height (inches) & Weight (pounds)

Each abnormality will be recorded, and the investigator will record an assessment of its clinical significance. **Any abnormality noted at SV1 should be listed on the medical history eCRF, if relevant.** If an abnormality presents later in the trial, it should be listed as an AE if it meets the criteria in Section 5.15.

### 5.6.1. Physical Examination

Only one of the following assessments is required to verify adequate perfusion of the affected limb; however, more than one test may be performed to determine eligibility. The assessment chosen is at the discretion of the investigator; however, the acceptability of parameters of each test must be followed as stated below.

#### 5.6.1.1. Ankle-Brachial Index (ABI)

ABI, if conducted, will be determined on the affected side (i.e., the side of the body on which the study ulcer resides) according to standard procedure/protocol at the study site.

If ABI is  $\geq 0.65$  or  $\leq 1.2$ , then vascular perfusion is considered adequate. An ABI measurement that has been collected within 3 months of screening is acceptable.

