SUBJECT ELIGIBILITY CRITERIA	
Inclusion Criteria
 
Subjects are required to meet all of the following criteria for enrollment into the study and subsequent randomization:
 
 
1. The subject has signed and dated an informed consent form.
 
2. In the opinion of the investigator, subject is able and willing to comply with study procedures, including study visits, study dressing regimens and compliance with study required off-loading device.
 
3. The subject is <math>\geq 18</math> years of age.
 
4. The subject, if female of child-bearing potential, must not be pregnant. To document pregnancy status, subject statement is acceptable.
 
5. The subject has Type I or Type II diabetes mellitus with investigator-confirmed glycosylated hemoglobin (HbA1c) of <math>\leq 12\%</math> within 3 months prior to screening visit 1.
 
6. The subject has at least one diabetic foot ulcer that meets ALL of the following criteria:             
 
• Ulcer which has been in existence for a minimum of two weeks, prior to signing the Informed Consent Form for trial participation.
 
• Ulcer is a partial or full thickness diabetic foot ulcer without capsule/tendon/bone exposure.
 
• Ulcer does not have tunneling, undermining, or sinus tracts that necessitates surgical OR debridement and/or penetrates to capsule/tendon/bone.
 
• Ulcer is located on the foot or ankle (with no portion above the top of the malleolus).
 
• Ulcer size (area) is <math>\geq 1</math> cm^2 and <math>\leq 12</math> cm^2 post-debridement.
 
 
 
7. There is a minimum 1 cm margin between the qualifying study ulcer and any other ulcer on that same foot, post-debridement.             
 
• If the subject has more than one ulcer that meets the eligibility criteria, the ulcer designated as the study ulcer will be at the discretion of the investigator.
 
 
 
8. The subject has adequate vascular perfusion of the affected limb as defined by at least one of the following:             
 
• Ankle-Brachial Index (ABI) <math>\geq 0.65</math> or <math>\leq 1.2</math>, performed within 3 months of screening,
 
• Toe pressure (plethysmography) <math>> 50</math> mmHg at time of screening,
 
• TcPO2 <math>> 40</math> mmHg at time of screening
 
 
 
9. The subject or responsible caregiver is willing and able to maintain required applicable dressing changes as well as study required off-loading/protective device for the duration of the study.
 
 
Exclusion Criteria
 
Subjects will not be enrolled in the study if any of the following criteria are met:
 
 
1. The subject was previously randomized and treated under this clinical study protocol.
 

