## 2. Study Objective

The objective of this study is to evaluate the efficacy of PriMatrix Dermal Repair Scaffold in the closure of DFUs in subjects with DM and without significantly compromised arterial circulation in comparison to Control treatment. In addition to the efficacy data, safety associated with the management of DFUs will be evaluated, as well as medical resource utilization data.

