## 3. Study Design

This is a multicenter, randomized, open-label, parallel-group clinical trial designed to establish the superior efficacy of PriMatrix over that of Control treatment in the management of DFUs in subjects with DM and adequate arterial circulation. Study enrollment will be paused once 50 subjects (25 in each treatment arm) have been enrolled in order to do an early data review. There will also be an interim analysis after 128 subjects have completed their study requirements.

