## 4. Study Population: Eligibility Criteria

### 4.1. Inclusion Criteria

Subjects are required to meet all of the following criteria for enrollment into the study and subsequent randomization:

1. The subject has signed and dated an informed consent form.
2. In the opinion of the investigator, subject is able and willing to comply with study procedures, including study visits, study dressing regimens and compliance with study required off-loading device.
3. The subject is  $\geq 18$  years of age.
4. The subject, if female of child-bearing potential, must not be pregnant. To document pregnancy status, subject statement is acceptable.
5. The subject has Type I or Type II diabetes mellitus with investigator-confirmed glycosylated hemoglobin (HbA1c) of  $\leq 12\%$  within 3 months prior to screening visit.
6. The subject has at least one diabetic foot ulcer that meets ALL of the following criteria:
  - Ulcer which has been in existence for a minimum of two weeks, prior to signing the Informed Consent Form for trial participation.
  - Ulcer is a partial or full thickness diabetic foot ulcer without capsule/tendon/bone exposure.
  - Ulcer does not have tunneling, undermining, or sinus tracts that necessitates surgical OR debridement and/or penetrates to capsule/tendon/bone.
  - Ulcer is located on the foot or ankle (with no portion above the top of the malleolus).
  - Ulcer size (area) is  $\geq 1 \text{ cm}^2$  and  $\leq 12 \text{ cm}^2$  post-debridement.
7. There is a minimum 1 cm margin between the qualifying study ulcer and any other ulcer on that same foot, post-debridement.
  - If the subject has more than one ulcer that meets the eligibility criteria, the ulcer designated as the study ulcer will be at the discretion of the investigator.
8. The subject has adequate vascular perfusion of the affected limb as defined by at least one of the following:
  - Ankle-Brachial Index (ABI)  $\geq 0.65$  or  $\leq 1.2$ , performed within 3 months of screening,
  - Toe pressure (plethysmography)  $> 50 \text{ mmHg}$  at time of screening,
  - TcPO2  $> 40 \text{ mmHg}$  at time of screening
9. The subject or responsible caregiver is willing and able to maintain required applicable dressing changes as well as study required off-loading/protective device for the duration of the study.

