#### 5.6.1.2. Systolic Pressure of the Great Toe

The systolic pressure of the great toe of the affected foot (i.e., the foot on which the study ulcer resides) will be obtained while the subject is sitting. If toe pressure is  $> 50\text{mmHg}$ , then vascular perfusion is considered adequate. This must be done at SV1; previous measurements are not accepted.

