#### 5.6.1.3. Transcutaneous Oxygen Pressure

Transcutaneous Oxygen Pressure (TcPO2) will be determined according to standard procedure/protocol at the study site. If TcPO2 is  $> 40\text{mmHg}$ , then vascular perfusion is considered adequate. This must be done at SV1; previous measurements are not accepted.

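### The ABI eligibility limits are joined by *or* in all three places, so no ABI value can fail, which contradicts the stated population with adequate arterial circulation

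*Protocol*

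**What the plan says.** Criterion 8 in Protocol Section 4.1 requires that "The subject has adequate vascular perfusion of the affected limb as defined by at least one of the following": ABI, toe pressure or TcPO2. The Synopsis version of the ABI item is "Ankle-Brachial Index (ABI) \geq 0.65 or \leq 1.2 , performed within 3 months of screening". Section 4.1 repeats it, and Section 5.6.1.1 restates it as "If ABI is $\geq 0.65$ or $\leq 1.2$ , then vascular perfusion is considered adequate".

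Section 5.6.1 says that only one test is needed, that more than one may be done, and that the investigator chooses. It adds that "the acceptability of parameters of each test must be followed as stated below". The other two tests each have a limit that a subject can fail: "If toe pressure is $> 50\text{mmHg}$ , then vascular perfusion is considered adequate" (Section 5.6.1.2) and "If TcPO 2 is $> 40\text{mmHg}$ , then vascular perfusion is considered adequate" (Section 5.6.1.3).

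The population is described in Section 2 as subjects "without significantly compromised arterial circulation in comparison to Control treatment" and in Section 3 by the aim of showing superiority "in the management of DFUs in subjects with DM and adequate arterial circulation". The SAP lists ABI as an abbreviation but gives no ABI limits.

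**The concern.** An eligibility limit should be able to exclude someone. Toe pressure and TcPO2 can; the ABI rule as written cannot. Since one passing test is sufficient, an ABI on record settles criterion 8 by itself, however low or high it is. The criterion that is meant to deliver the population named in the objective then does no work for those subjects.

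What is at stake is the description of the trial population. A report of efficacy in adequately perfused limbs should be able to show that the subjects met a perfusion standard. A subject admitted under the literal wording met the criterion, so the protocol deviation listing in SAP 12.2.1 need not show that subject.

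**Working it through.** The plan gives no figure to reproduce. This is a check of logic, followed by a check of what the SAP would report.

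**Inputs.** ABI limits 0.65 and 1.2, joined by *or* (Synopsis criterion 8, Section 4.1 criterion 8, Section 5.6.1.1). Toe pressure above 50 mmHg (5.6.1.2). TcPO2 above 40 mmHg (5.6.1.3). Any one test suffices (4.1, 5.6.1).

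**Step 1: the ABI rule.** A value passes if ABI ≥ 0.65 or ABI ≤ 1.2. To fail, it would have to be both below 0.65 and above 1.2. Since 0.65 < 1.2, no such value exists. Examples:

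| ABI | ≥ 0.65 | ≤ 1.2 | Result as written |
|---|---|---|---|
| 0.40 | no | yes | passes |
| 1.00 | yes | yes | passes |
| 1.40 | yes | no | passes |

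On a grid from 0.00 to 3.00 in steps of 0.01 there are 3.00/0.01 + 1 = 301 values, and 301 of 301 pass. The values that satisfy both limits number (1.20 − 0.65)/0.01 + 1 = 56. The grid is an assumed range, not a patient distribution. The result that nothing fails does not depend on it.

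**Step 2: criterion 8.** The criterion is met if ABI passes, or toe pressure passes, or TcPO2 passes. With an ABI on record the first term is always true, so the criterion is always met. Without an ABI, the subject must still pass toe pressure or TcPO2, so the criterion is empty only for subjects who have an ABI.

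**Step 3: whether another passage closes the gap.**
- Exclusion 8 (Section 4.2) relies on the investigator's opinion and sets no perfusion limit.
- The randomization screen (Section 5.16) asks a general eligibility question and then checks area reduction and ulcer area. It asks for no perfusion value.

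**Step 4: what would be reported.**
- Perfusion tests are among the data to be collected (Synopsis, Data Collection), and Protocol 8.7 and SAP 12.1 commit to listing all collected data by subject. Individual values are therefore already due to be listed.
- Perfusion is not among the named baseline variables (SAP 12.2.2) or prognostic factors (SAP 11.4).
- The physical examination summary in SAP 12.2.2 might take in ABI, but the visit list (Protocol 6.1.1) and both schedules of events treat vascular perfusion as a separate item.
- No planned table counts which test qualified each subject.

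**Step 5: effect on inference.** The rule applies before randomization and identically to both arms. The sample size rests on assumed closure rates of 46% and 26% with no perfusion term, and the documents give no closure rates by ABI, so no power effect can be derived.

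**The case against.** The sponsor could fairly reply that this is a drafting slip with one sensible reading. Two limits in one bullet, under a stem about adequate perfusion, suggest a range, and sites may have applied one. If they did, subjects outside it would have been recorded as deviations and listed. Other provisions also narrow the opening: exclusion 2 (gangrene), exclusion 6 (recent or scheduled vascular surgery, angioplasty or thrombolysis), and the screening examination of the extremities and cardiovascular system. Individual values will be listed in any case, and enrolment has ended (SAP 10.4).

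Most of this stands and limits the point. A slip is the likely explanation, and no new listing is needed. But Section 5.6.1 binds sites to the limits as stated, Section 10.3 obliges investigators to follow the written requirements, and the same wording appears three times without correction. None of the other provisions sets an ABI limit.

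A reader might infer more than the documents support:
- **That poorly perfused subjects were enrolled.** The documents contain no ABI data and do not show this.
- **That the treatment comparison is biased or Type I error inflated.** A rule applied before randomization, and equally to both arms, does neither.
- **That the *or* is what lets a subject qualify after failing toe pressure and TcPO2.** That follows from the rule that any one test suffices. It would remain possible under a range reading for a subject whose ABI lay within the range.
- **That excluding subjects on ABI is automatically neutral because ABI precedes randomization.** The value does, but the rule would be confirmed only now, in an open-label trial with enrolment closed. Neutrality depends on fixing the rule before ABI is reviewed against arm or outcome.

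**Conclusion.** The point holds as an error in an eligibility threshold. As written, the ABI rule excludes no value, and any subject with an affected-side ABI within 3 months of screening meets criterion 8. This conflicts with Sections 2 and 3 of the Protocol. The logic rests on no assumption about data, alpha or power.

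Its practical size is unknown: of the 207 subjects that SAP 11.1.1 expects in the primary efficacy population, the number who qualified on ABI alone outside the intended rule may be zero. The consequence is limited to whom the result describes. It should be put right, because the trial relies on this threshold to define its population and the correction is cheap.

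**What to change.** 1. The sponsor reconciles the Synopsis, Section 4.1 and Section 5.6.1.1 with each other and with the objective, and documents the intended ABI rule. This must be done before anyone reviews ABI values against arm or outcome. No limit is proposed here.
2. Add to the SAP a by-arm count of the perfusion test on which each subject qualified, and of subjects who qualified on ABI alone with a value outside the documented rule.
3. If there are any such subjects, add one sensitivity analysis of the primary endpoint without them, labelled as specified after enrolment closed.
4. Leave the primary and per-protocol populations unchanged, since these subjects met the text as written.

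The cost is one documented clarification covering three passages, one table from data already collected, and at most one further analysis. No new data are needed, and rewording cannot change who was randomized.

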#### 5.6.1.2. Systolic Pressure of the Great Toe

The systolic pressure of the great toe of the affected foot (i.e., the foot on which the study ulcer resides) will be obtained while the subject is sitting. If toe pressure is  $> 50\text{mmHg}$ , then vascular perfusion is considered adequate. This must be done at SV1; previous measurements are not accepted.

#### 5.6.1.3. Transcutaneous Oxygen Pressure

Transcutaneous Oxygen Pressure (TcPO2) will be determined according to standard procedure/protocol at the study site. If TcPO2 is  $> 40\text{mmHg}$ , then vascular perfusion is considered adequate. This must be done at SV1; previous measurements are not accepted.

#### 5.6.2. Number and Location of Study Ulcer(s)

The number and location of any and all DFUs will be documented during the physical exam.

### 5.7. Ulcer Assessments

#### 5.7.1. Extent and Location of Ulceration

On SV1, the date that the ulcer was first observed will be documented.

Documentation of tunneling, undermining, or sinus tracts that necessitates surgical debridement in the OR and/or penetrates to capsule/tendon/bone is required. Additionally, a determination of whether the ulcer is partial or full thickness and if there is exposure of capsule, tendon, or bone will be documented.

The location of the study ulcer will be documented according to foot (left or right), surface (plantar or dorsal), and area (forefoot, midfoot, hindfoot [with the hindfoot area to include the calcaneus], ankle [with no portion above the top of the malleolus]).

If the subject has more than one qualifying DFU, the ulcer designated as the study ulcer will be at the discretion of the investigator.

### 5.7.2. Ulcer Exudate Assessments

The investigator will determine the amount and type, if any, of study ulcer exudate. In determining the amount of study ulcer exudate, the investigator must take into account the amount of exudate absorbed into the study ulcer dressing. The following categories will be used to quantify the amount of ulcer exudate:

- Not applicable: No exudate
- Minimal amount
- Light (scant) or small amount
- Moderate amount
- Heavy/large/copious amounts

The following categories will be used to describe the type of exudate:

- Serous: clear or light yellow watery plasma
- Serosanguineous: pink to light-red watery plasma
- Sanguineous: red with fresh bleeding
- Purulent: thick and opaque exudate, of creamy yellow, green, white, or tan color

### 5.7.3. Ulcer Infection Assessment

The presence/absence of infection at the study ulcer site will be documented at each visit.

**IMPORTANT:** If the study ulcer is considered infected during the screening phase, or at Randomization visit (TV1), the subject is considered a screen fail and is excluded from participation in the trial at that time. The infection must be treated, and symptoms resolved before the subject may be re-screened (one time only, according to Section 6.1.2). Additionally, and per exclusion criterion 2, the subject must not be taking antibiotics for a DFU infection.

If the study ulcer becomes infected after the subject is randomized, it must be recorded as an AE. The study ulcer infection may be treated, per investigator judgement, and the subject may remain in the study unless a prohibited medication or treatment is used (see Section 5.14.1).

*PriMatrix is contraindicated for infected ulcers.* In the event of a study ulcer infection in the PriMatrix treatment group, PriMatrix may be re-applied after the study ulcer infection has been treated and no longer demonstrates signs/symptoms of the infection.

All infections will be followed until resolved or the subject is withdrawn or discontinued. If an infection progresses to tissue necrosis requiring deep debridement which exposes bone, tendon or capsule, the subject must be withdrawn.

In no case, does the presentation of infection alter the study schedule of events nor allow the subject additional days of treatment.

## 5.8. Study Ulcer Photography

Photographs of the study ulcer are required at each visit except Unscheduled Visits. The investigator will take a digital photograph using the study-supplied imaging system. **At minimum, pre-debridement photographs of the study ulcer are to be taken at every visit.**

